#### **8.8. Visit 10 – (Month 18 ± 14 days of stimulation)**

Visit 10 will occur after 18 months of stimulation (including lead-in portion of the FREEOAB study). This visit may be conducted remotely via ePRO.

Step	Action
1.	Subjects will be queried for AE/SAE or concomitant medication changes.
2.	The 3-day Bladder Diary dispensed at Visit 9 will be collected and reviewed.
3.	Applicable visit forms and questionnaires will be completed
4.	Subjects will be given a new 3-day Bladder Diary to complete within 3 days leading up to their next scheduled visit.

#### **8.9. Visit 11 – (Month 24 ± 14 days of stimulation) – End of Study**

Visit 11 will occur after 24 months of stimulation.

Step	Action
1.	Subjects will be queried for AE/SAE or concomitant medication changes.
2.	The 3-day Bladder Diary dispensed at Visit 8 will be collected and reviewed
3.	Applicable visit forms and questionnaires will be completed
4.	Subjects will return their study equipment and supplies to the site staff and exit the from the study.

## 8.10. Unscheduled Visits

Unscheduled visits are permitted to occur as needed, for the purposes of resolving issues, AE/SAE follow up, and may be performed remotely or in-clinic, depending on the reason for the visit.

## 8.11. Visit Schedule for Long-Term Follow-Up Phase

	Visit 6	Visit 7	Visit 8	Visit 9	Visit 10	Visit 11
Study Phase	enrollment	Month 6	Month 9	Month 12	Month 18	Month 24
Informed Consent	X					
3-day Bladder Diary (a,b)	X	X	X	X	X	X
Inclusion/Exclusion Check	X					
OAB-q				X		X
IIQ-7				X		X
I-QoL				X		X
PGIC		X	X	X	X	X
OHQ				X		X
Study Visit Form	X	X	X	X	X	X
Exit Form						X

a - 3-Day Bladder Diary to be dispensed at Visit 6, Visit 7, Visit 8, Visit 9, and Visit 10.

b - 3-Day Bladder Diary to be collected at Visit 7, Visit 8, Visit 9, Visit 10, and Visit 11.

## 9. Outcome Variables

All outcome variables will be collected by the investigator.

### 9.1. Demographics

Basic subject demographics will be collected such as height, weight, race, and ethnicity.

### 9.2. Study Visit Form

This form asks questions regarding comfort, tolerability, and satisfaction of the Test Article as well as comfort and tolerability of the therapy.

### 9.3. Test Article Assessment Form

The subject will be asked several questions regarding the Test Article, specifically ease of use and comfort.

### 9.4. IIQ-7

The IIQ-7 questionnaire asks subjects about areas of their life that may have been influenced or changed by incontinence. It looks at its effect on activities, relationships, and feelings.

### 9.5. I-QOL

The incontinence quality of life questionnaire is used to assess the quality of life in subjects with urinary incontinence due to neurogenic detrusor overactivity [5].

### 9.6. OAB-q

This questionnaire asks about how much you have been bothered by selected bladder symptoms during the past 4 weeks.

## 9.7. PGIC

The Subject global impression of change evaluates all aspects of Subjects' health and assesses if there has been an improvement or decline in clinical status.

## 9.8. OHQ

This questionnaire assesses the level of happiness experienced by the Subject by asking them to rate a series of statements based on their level of agreement.

## 10. Test Article

The Test Article consists of a garment, a stimulator, gel pads, a controller, and charging system.

### 10.1. Garment, Stimulator, Charger, and Gel Pads

The Garment is worn on the foot and ankle area to provide a comfortable and convenient method of holding the electrodes in the desired location and a place to hold the stimulator. The stimulator unit can be easily removed to allow recharging. Replaceable gel pads are located inside the Garment to improve skin contact. Gel Pads can be replaced. The stimulator will have an on/off button and LED's to indicate Bluetooth connection status and battery level.

Figure 1 Wearable tibial nerve stimulation garment with built-in stimulating and sensing electrodes, fits left & right ankles

### 10.2. Material

Article	Material
Garment	Neoprene
Stimulator and Charger	3D Printed Plastic (ABS-Like)
Gel Pads	Hydrogel

### 10.3. Stimulation Specifications

[figure not shown]
Parameters	Technical Description
Pulse Type	Charged balanced biphasic
Output	Current-controlled
Number of stimulation electrodes	2 (one cathode, one anode)

Number of recording electrodes	3 ( two differential inputs, one reference input)
Maximum current amplitude	40 mA
Maximum output voltage	200 V
Maximum pulse width per phase	800 us
Maximum pulse frequency	20 Hz
Worst-case current density per phase	7.8 mA/ cm 
Worst-case charge density per phase	3.1 uC/cm 
Power Source	Lithium-ion battery
Connection to mains power	None

#### 10.4. Controller

The Stimulator will be controlled using an application on a tablet. This tablet will be supplied by the Sponsor and will only be enabled as a controller for the stimulator.

The controller application will have screens which will allow both the physician and subject to easily interact with the stimulator. Data collected by the stimulator will be transmitted to a HIPAA-compliant cloud to allow the investigators and Sponsor to easily review the subject's usage of the system while completing their treatment sessions at home. This will also allow troubleshooting to take place without a visit to the office.

## 11. Regulatory Status

The Test Article is not approved for sale in any country.

## 12. Safety and adverse events

### 12.1. Definitions

Adverse Events (AE)	Any untoward medical occurrence, unintended disease or injury, or untoward clinical signs (including abnormal laboratory findings) in subjects, users, or other persons, whether or not related to the investigational medical device.
Serious Adverse Events (SAE)	A current adverse event that worsened or the occurrence of a new adverse event that: a) led to death b) led to serious deterioration in the health of the subject, that either resulted in: 1) a life-threatening illness or injury, or 2) a permanent impairment of a body structure or a body function, or 3) in-patient or prolonged hospitalization, or 4) medical or surgical intervention to prevent life-threatening illness or injury or permanent impairment to a body structure or a body function c) led to fetal distress, fetal death or a congenital abnormality or birth defect
Unanticipated Adverse Device Effect (UADE)	Adverse device effect which by its nature, incidence, severity or outcome has not been identified in the current version of the risk analysis report.
Unanticipated Serious Adverse Device Effect (USADE)	Serious adverse device effect which by its nature, incidence, severity or outcome has not been identified in the current version of the risk analysis report.

### 12.2. AE Recording

All AEs or UADEs volunteered by the subjects or elicited by the Investigator must be recorded on the appropriate AE CRF. In accordance with the medical device incident reporting and investigation scheme (IRIS) (in the US follow 21 CFR 812.150(a)(1)), an Investigator shall submit to the Sponsor and IRB a report of any UADE occurring during the investigation as soon as possible, but no later than 10 days after the Investigator first learns of the event. Unanticipated Serious Adverse Device Effect (USADEs) will be reported to the regulatory authorities as required. This report must be confirmed by using the AE source documentation and eCRF data.

### **12.3. Reporting AEs**

Qualified investigators and research staff will closely and carefully monitor study participants for all anticipated and any unanticipated adverse events. All serious and device related adverse events or device deficiency should be recorded on the appropriate case report form. All adverse events will be reported from the moment a consented participant is in contact with the study device, through to participant study exit. Investigational sites will be asked to report the final medical diagnosis as an AE, rather than reporting all signs and symptoms as separate events.

It is the responsibility of the investigator to decide when an adverse event has occurred. Adverse event information will be collected throughout the study. Adverse events will be recorded on the appropriate CRF by the investigator or study coordinator. Event, date of onset, severity, duration and relationship to the procedure or device will be recorded.

In case of a serious adverse event (whether or not related to the investigational device), or an unanticipated adverse device effect, the investigator should complete the applicable SAE CRF pages within 24 hours of being made aware of the event and begin the reporting process. If the case report form cannot be completed within 24 hours, the Investigator should advise the Sponsor by other means, within 24 hours.

The Sponsor will assist the site with reporting any SAEs to the reviewing ethics committee, according to their requirements and timelines.

All SAEs and UADEs must be reported to and reviewed by the Sponsor.

NOTE: As applicable, reports must only identify participants using the study's unique identifier to protect confidentiality.

Non-serious AEs should be reported at the next routine contact.

### **12.4. Anticipated Adverse Events and Complications**

The anticipated AEs associated with using the Test Article include:

1. Pain at the stimulation site.
2. Allergic reaction.
3. Changes in skin color (reddening) under the electrode.

### **12.5. AE Classification**

The Investigator will classify each AE according to the Adverse Event Form. If the AE is serious or the Investigator feels that the device contributed in any way to the AE, the Investigator must report the event to the Sponsor.

## **13. Data Analysis, Evaluation and Statistical Plan**

### **13.1. Analysis Populations**

Analyses will be performed within both the intent-to-treat (ITT) population of all enrolled patients and among the subset of patients who complete the study. Patients may be missing endpoint data at one or more, or possibly all, post-screening time points, at which endpoint data will be provided by carrying forward the most recent observation. Enrollment will continue until 80 subjects complete the study. Expecting 15% dropout, the anticipated total enrollment will be approximately 94 patients.

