Study design	
Subjects that have signed the Informed Consent Form and meet all applicable eligibility criteria will be randomized 1:1 to 30-minute stimulation treatments either once a week or three times a week over a treatment period of 12 weeks.
 
Subjects will return to the clinic at 1-, 4-, 8-, and 12-weeks post-baseline for visit assessments listed in the Schedule of Activities. Investigative sites may elect to have some visits completed remotely via use of ePRO for visit questionnaires. On weeks where a subject does not have an in-clinic visit, they will be contacted by phone and queried for health and medication changes and any device issues. At the end of the first 12 weeks of stimulation, subjects will return to the clinic for final assessments, then will either enroll in the long-term follow up phase, if eligible, or exit from the study.

Statistical Methods	
Analyses will be performed within both the intent-to-treat (ITT) population of all enrolled patients and among the subset of patients who complete the study. Patients may be missing endpoint data at one or more, or possibly all, post-screening time points, at which endpoint data will be provided by carrying forward the most recent observation. Enrollment will continue until 80 patients complete the study. Expecting 15% dropout, the anticipated total enrollment will be approximately 94 patients.

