### **13.2. Analysis of Efficacy and Sample Size**

Using data collected at each of Study Visits 2, 3, and 4, percent change from screening at each time point will be calculated for each patient with respect to frequency of OAB symptoms, including 3-day daily averages of daytime voids, urge events, nighttime voids, and urge incontinent events. The maximum percent improvement across the four symptoms will also be calculated at each time point as a composite endpoint. Percent improvement in daily average total voids relative to an upper normal limit of 8, will also be calculated, and will be bounded below at 0% for patients not achieving improvement and bounded above at 100% for patients achieving or surpassing the upper normal limit of 8. Longitudinal analyses will be performed using repeated measures models to assess and describe trends over time with respect to these endpoints. At individual time points, the one-sample T-test will be performed at significance level  $\alpha=0.05$  within each treatment group and for the pooled study groups to assess the mean percent improvements, with 95% confidence intervals for mean percent improvements also calculated. The percent change endpoints are not likely to have approximately normal distributions, but the sample size is considered sufficient such that mean values will be approximately normally distributed, justifying the use of the T-tests. If there is concern with the distributions, then the Wilcoxon signed rank test will be used as an alternative to the one-sample T-test.

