Sample size is evaluated by the performance of the 95% confidence interval for mean percent improvement percent improvement in daily average total voids relative to an upper normal limit of 8. Log ratios of daily average event frequencies at post-screening time points relative to the daily average event frequencies at baseline, which are mathematically related to the percent changes from baseline, are more likely than percent changes to have approximately normal distributions. If such log ratios are normally distributed so that in both treatment groups the median percent improvement (toward zero) in daily average total voids is 15% and so that 25% of patients will achieve a 50% improvement, then with a total evaluable sample size of 80 patients completing the study, there is an estimated 95.6% power to conclude that the mean percent improvement in daily average total voids relative to an upper normal limit of 8 is 25% or larger using the 95% confidence interval. Within each treatment group of size  $n=40$ , there is an estimated 90.8% power to conclude that the mean percent improvement in daily average total voids relative to an upper normal limit of 8 is 20% or larger using the 95% confidence interval.

Two-sample T-tests performed at a significance level  $\alpha=0.05$  will be used to compare the treatment groups with respect to mean percent improvements in frequency of OAB symptoms, and with respect to results of OAB questionnaires. If there is concern with the non-normality of the distributions of these endpoints, then the Wilcoxon rank sum test will be used as an alternative to the two-sample T-test. Linear models will be constructed as extensions of the one-sample and two-sample T-tests to allow for assessments of mean percent improvements and group comparisons with covariate adjustments.

Frequencies of responders at individual time points and over all time points will also be calculated, where a responder for a given OAB symptom is defined as a subject achieving 50% improvement in frequency, and a responder for the composite collection of OAB symptoms is defined as a subject achieving 50% improvement in frequency for at least one symptom frequency. The treatment groups will be

compared with respect to response frequencies using chi-square or Fisher's exact tests, and exact 95% binomial confidence intervals will be calculated.

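### LOCF is the only rule for missing visits. It reaches patients with screening data only and does not exempt the repeated-measures models, so ITT means and trends can be biased, in a direction the documents do not fix

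*Combined protocol and SAP*

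**What the plan says.** Section 13.1 expects gaps: "Patients may be missing endpoint data at one or more, or possibly all, post-screening time points". It fills them by one rule, as time points "at which endpoint data will be provided by carrying forward the most recent observation". The Statistical Methods row of the protocol summary (Section 2) repeats it: "endpoint data will be provided by carrying forward the most recent observation". Two populations are planned, all enrolled patients (ITT) and an analysis "among the subset of patients who complete the study". Neither is named primary. Enrolment runs until 80 complete; with 15% dropout about 94 are expected.

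Section 13.2 opens "Using data collected at each of Study Visits 2, 3, and 4" and defines percent change from screening for each symptom. It also defines an improvement in total voids relative to a normal limit of 8, bounded at 0% and 100%. It then says "Longitudinal analyses will be performed using repeated measures models to assess and describe trends over time". One- and two-sample t-tests, linear models and responder comparisons follow. None is said to use observed data only. No missing-data assumption, target of estimation or missing-data sensitivity analysis is stated.

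**The concern.** LOCF treats the last value as what would have been measured later. A patient with screening data only has nothing to carry but the screening diary, so that patient counts as 0% improvement at every visit. Read as written, the copied values also enter the repeated-measures models, where they flatten the estimated course.

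The protocol's own rationale makes a flat course doubtful. For PTNS, the analogous therapy, Section 17.2 says that symptoms usually take 5 to 7 weeks to change and that relief began anywhere from 2 to 12 weeks. If this device acts similarly, an early value understates the later effect. If benefit is lost after stopping, a carried value overstates the outcome. The sample size in Section 13.2 rests on a confidence interval for a mean, so the mean is the quantity at stake.

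**Working it through.** **The plan's own figures.** Enrolment: 80/0.85 = 94.1, which agrees with about 94. For power, Section 13.2 assumes a 15% median improvement, so the mean log ratio is ln 0.85 = -0.1625, and that "25% of patients will achieve a 50% improvement", so the SD is ln(0.85/0.50)/0.6745 = 0.787. With baseline B and ratio r of post-screening to screening voids, the bounded endpoint is B(1 - r)/(B - 8), limited to 0 to 1. B is not stated. Simulated power for n = 80 against 25% and n = 40 against 20%:

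| B (voids/day) | n = 80 | n = 40 |
|---|---|---|
| 12 | 99.6% | 97.5% |
| 14 | 98.6% | 95.1% |
| 16 | 96.3% | 91.8% |
| 16.5 | 95.6% | 91.1% |
| 17 | 94.7% | 90.0% |

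Section 13.2 says "there is an estimated 95.6% power to conclude" for the first and gives 90.8% for the second. B = 16.5 fits best and is used below.

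**Assumptions for the bias.** The log effect builds in proportion to time and reaches the Section 13.2 values at Week 12. Diary error SD on the log scale is 0.15 or 0.30. Dropout is 15%. Bounded means:

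| Diary SD | Week 1 | Week 4 | Week 8 (Visit 4) | Week 12 |
|---|---|---|---|---|
| 0.15 | 12.6% | 23.7% | 35.8% | 42.4% |
| 0.30 | 20.8% | 27.5% | 36.5% | 42.4% |

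**Even dropout, unrelated to outcome, target had all continued.** 3.75% leave after each of screening, Week 1, Week 4 and Week 8.
- Visit 4: 0.0375 × (0 + 12.6 + 23.7 - 3 × 35.8) = -2.7 points; with SD 0.30, 0.0375 × (0 + 20.8 + 27.5 - 3 × 36.5) = -2.3. Simulated coverage of the 95% interval is 88 to 91%.
- Week 12, if analysed: 0.15 × (18.0 - 42.4) = -3.7; with SD 0.30, 0.15 × (21.2 - 42.4) = -3.2. Here 18.0 and 21.2 are the means of 0 and the Week 1, 4 and 8 values. Coverage is 86 to 89%.
- Trend, Week 1 to Visit 4 (SD 0.15): LOCF gives 12.6 × 0.9625 = 12.1 and 35.8 - 2.7 = 33.1. The rise is 21.0 points instead of 23.2, about 10% too small.

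**Other timing, same target.**
- All leave after Week 8: 0 at Visit 4; at Week 12, 0.15 × (35.8 - 42.4) = -1.0 or 0.15 × (36.5 - 42.4) = -0.9.
- All have screening data only (extreme): -0.15 × 35.8 = -5.4 or -0.15 × 36.5 = -5.5 at Visit 4; -0.15 × 42.4 = -6.4 at Week 12.
- Full effect from Week 1, even dropout: -0.0375 × 42.4 = -1.6.

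**Return to screening level, target regardless of stopping, even dropout.**
- Visit 4, LOCF: 0.0375 × (12.6 + 23.7) = +1.4 or 0.0375 × (20.8 + 27.5) = +1.8.
- Visit 4, missing-at-random or completers: 0.1125 × 35.8 = +4.0 or 0.1125 × 36.5 = +4.1.
- Week 12: LOCF 0.15 × 18.0 = +2.7 or 0.15 × 21.2 = +3.2; the others 0.15 × 42.4 = +6.4.

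**Does the completer analysis expose the problem?** Assume that the odds of leaving are multiplied by 2 to 3 per SD worse at the last diary (2,500 simulated trials per setting, 47 per arm, target had all continued). At Visit 4, LOCF is off by -2.4 to -2.8, completers by +1.7 to +2.7, and multiple imputation by group by +0.1 to +0.3. Neither planned analysis is then centred on the target.

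**Arm comparison, no true difference, 10% versus 20% even dropout.** False difference at Visit 4: 0.10 × (35.8 - 18.0) = 1.8 or 0.10 × (36.5 - 21.2) = 1.5 points. At Week 12 it is 2.1 to 2.4. Type I error is 5.0 to 5.7%. A far larger assumed imbalance, 5% versus 25% (checked at Week 12 with B = 16 and a faster build-up), gives 6.6%, or 15.2% if every dropout has screening data only.

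**Standard error.** The simulated LOCF standard error matches the spread of its own estimate: 3.93 against 3.89 at Visit 4 and 4.38 against 4.41 at Week 12. The coverage loss therefore comes from the bias.

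**The case against.** The strongest reply is that bias needs a target and the plan names none. An ITT label fits the outcome regardless of stopping at least as well as the mean had all continued. Under the first target, with benefit lost after stopping, LOCF does better than missing at random. That stands: the plan must choose, and missing at random is not simply the better method.

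Three further points stand in part.
- If the effect builds, LOCF pulls the mean toward zero, which is conservative against the 25% and 20% thresholds. It is not conservative in the return-to-screening case.
- The build-up and the constant, back-fitted baseline are assumptions, and the onset evidence concerns PTNS. The claim is therefore that the means can be biased, with a range.
- That copied values enter the repeated-measures models is inferred from silence, and no such model was fitted here. Still, Section 13.1 states its rule without exception.

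Remote visits and weekly calls (Section 7.2) and the effort to obtain follow-up data (Section 14) should limit the gaps, but the plan still budgets 15% dropout.

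A reader might also infer that the intervals are too narrow because about 94 values are counted where 80 were measured, 1 - √(80/94) = 7.7%. This fails for the single-visit t-tests. Each patient contributes one value, and the standard error is right for the mean of those values; that mean may be off target.

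**Conclusion.** The point holds as a cheap improvement. LOCF is the only stated rule, it covers patients with screening data only, and nothing exempts the repeated-measures models. Under even 15% dropout unrelated to outcome, proportional build-up and 16.5 voids/day at baseline, the pooled bounded mean is about 2.3 to 2.7 points too low at Visit 4, and about 3.2 to 3.7 at Week 12 if that visit is analysed. The Visit 4 bias is 0 if all dropouts leave after Week 8. It turns to +1.4 to +1.8 if dropouts return to screening level and the target is the outcome regardless of stopping. The completer analysis is not a sufficient check, because it is itself biased when dropout depends on response.

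Two stronger inferences are not supported. The arm comparison is not shown to be unsound: it moves little at 10% versus 20% dropout, and nothing in the documents points to the extreme imbalance that would move it more. The stated power is not overstated by LOCF either, because it is for 80 completers. The absence of Visit 5 from the visits listed in Section 13.2 is a separate point and adds no weight here.

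**What to change.** In Section 13.1 and the protocol summary, replace the LOCF sentence with text to this effect:

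> The target of the ITT analysis is [the mean had all subjects continued assigned treatment / the mean regardless of stopping]. No carried-forward value enters the main analysis as a measurement. The repeated-measures models are fitted by likelihood to the observed diary data with the screening value included, or missing diary averages are multiply imputed by group under missing at random and the endpoints derived afterwards. Visit means, confidence intervals and the arm comparison come from that analysis. LOCF and completer analyses are secondary. A sensitivity analysis returns dropouts to their screening value, varied by arm; it becomes the main analysis if the target is regardless of stopping. A responder sensitivity analysis counts missing as non-response.

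The bounded and responder endpoints are non-linear in the diary counts, so imputing the diary averages first is the simpler route for them. It needs a method that allows zero counts. The simulation tested normal imputation of total voids on the log scale only, so its results do not vouch for the other endpoints.

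The cost is SAP wording and some programming; visits, data collection and sample size do not change. If the target is the mean had all continued, the main analysis then rests on missing at random. Intervals are also somewhat wider: in the simulation the Visit 4 standard error rose from 3.93 to 4.21 or from 4.02 to 4.33, about 7 to 8%.
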